Based on expert's knowledge, we find a 1 week lead in the functional recovery of the motor experimental group on the control group a clinically significant difference. With use of the mathematical model, the change in the PRWHE-score after 1 week after cast removal could be estimated. Next, the mean standard deviation of the PRWHE-scores over time was calculated. By dividing the change in the PRWHE-score by the mean standard deviation, the effect size was calculated. Now, the sample size could be calculated using the statistical power analysis software G*Power 3 (62).

Effect size calculation

The model describing the change in the PRWHE-score as result of natural recovery following a DRF, showed that 1 week after cast removal a decrease of 5.3 points on the PRWHE can be expected, which indicates improved function. This would mean that the experimental group would show an extra decrease of 5 points on the PRWHE, two weeks after cast removal.

The mean standard deviation was calculated using the following formula:

$$\sigma = \sqrt{\frac{n_x^2 s_x^2 + n_y^2 s_y^2 - n_y s_x^2 - n_x s_y^2 - n_x s_x^2 - n_x s_y^2 + n_y n_x s_x^2 + n_y n_x s_y^2 + n_x n_y (\bar{X} - \bar{Y})^2}{(n_x + n_y - 1)(n_x + n_y)}}$$

This provided a mean standard deviation of 26.13... points.

The effect size was calculated using the following formula:

$$ES = \frac{\mu_1 - \mu_2}{\sigma}$$

This provided an effect size of 0.20...

Settings for sample size calculation

Test Family: F-tests

Statistical test: Repeated Measures ANOVA, within-between interaction

Effect size: 0.20

Significance level $\alpha = 5\%$

Preferred power = 80%

Number of groups: 2

Number of measurements: 2

Other settings were kept as the default setting.

Sample size calculation

The effect size, preferred power, significance level and two-tailed testing were entered in

G*Power 3. Running the program resulted in a calculated sample size of 52 patients.

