9. STATISTICAL ANALYSIS

9.1 *Descriptive statistics*

Patient characteristics are presented using descriptive statistics for the potential confounding variables.

Data of the main outcome measure are of interval level of measurement. The ROM and grip strength are of ratio level of measurement. Hence, the descriptive statistics of these outcome measures are presented by the mean and standard deviation. Dexterity is measured using the SODA, and the data of this instrument are of ordinal level of measurement. Therefore, the descriptive statistics are presented by the median and range. Pain is measured using the VAS, which provides data of interval level of measurement. So, the descriptive statistics are presented by the mean and standard deviation.

9.2 *Univariate analysis*

The effectiveness of motor imagery training will be determined with use of a multivariate analysis for the parametric data (as described later in chapter 9.3). The non-parametric data are analyzed using a Mann-Whitney U test for each variable, to determine whether the groups are different. This test is also used when the data is not normally distributed.

9.3 *Multivariate analysis*

With use of a MANOVA, the difference between the experimental and control group will be determined for each measurement time and for each variable. There are two factors included in the analysis; a between factor 'group' and a within factor 'time'. The hypothesis is tested using two-tailed tests, with a significance level of 5%. The data of the patients in both groups will be analyzed using an intention to treat analysis.

9.4 *Interim analysis (if applicable)*

An interim analysis will be conducted to determine the effect of motor imagery training on hand function, dexterity, ROM, grip strength and pain. When the results of this analysis shows serious unwanted effects of motor imagery training, this study will be terminated.

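### The sample size of 52 treats a standardised mean difference of 0.20 as Cohen's f; power for the 5-point target is 10–11%, not 80%

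*Combined protocol and SAP*

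**What the plan says.** All the inputs are in section 4.4. A model of natural recovery puts one week's improvement at 5.3 PRWHE points. A 1-week lead is taken as the clinically significant difference, so the experimental group is expected to be about 5 points better two weeks after cast removal. The spread is given as: "This provided a mean standard deviation of 26.13... points". The effect size is a mean difference over an SD: "By dividing the change in the PRWHE-score by the mean standard deviation, the effect size was calculated".

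The G*Power settings are an F-test, "Statistical test: Repeated Measures ANOVA, within-between interaction", with "Effect size: 0.20", two groups, two measurements, two-sided 5% significance and "Preferred power = 80" per cent. The other settings were left at their defaults, and the correlation between visits is not stated. The result is: "Running the program resulted in a calculated sample size of 52 patients".

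Section 9.3 plans a MANOVA with group and time as factors, tested two-sided at 5%. Section 9 plans no confidence interval.

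**The concern.** The two effect sizes are on different scales. The protocol's formula, (μ1 − μ2)/σ, gives Cohen's d. The within-between interaction test in the F family takes Cohen's f, which is the SD of the interaction cell effects divided by σ. For two groups and two visits, f is much smaller than d for the same difference in points. Entering d in place of f therefore makes the required sample far too small.

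The PRWHE is the primary outcome, and the 5-point target is the protocol's own threshold for clinical significance. If 52 does not carry 80% power for it, a non-significant result could be taken as evidence against a 1-week lead when the trial had little chance of detecting one.

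**Working it through.** **Inputs (section 4.4 unless noted).** D = 5.3 points from the model, 5 points as the stated target; σ = 26.13; two-sided α = 0.05; 2 groups; m = 2 visits; N = 52, equal groups (section 7.2), so 26 per arm. Assumed, because only defaults are mentioned: correlation between visits ρ = 0.5 and nonsphericity ε = 1.

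**1. Effect size as defined.** 5.3/26.13 = 0.203 (5/26.13 = 0.191), which is d.

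**2. Reproducing 52.** In the G*Power parameterisation, λ = f²·N·m·ε/(1 − ρ), with 1 and N − 2 degrees of freedom. With f = 0.20:

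- N = 52: λ = 0.04 × 52 × 2/0.5 = 8.32, power 80.7%.
- N = 50: power 79.1%.

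So 52 is the smallest even total that reaches 80%. Other readings do not give 52. A two-sample comparison with d = 0.20 needs 788, and the interaction formula without ρ (λ = f²N) needs 200. The value 0.20 was therefore used as f.

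**3. The f that matches the target.** Take no group difference at the first visit (T1) and a difference D at the second (T2). The interaction cell effects are then ±D/4, so f = D/(4σ):

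- 5.3/(4 × 26.13) = 0.051
- 5/(4 × 26.13) = 0.048

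Conversely, f = 0.20 stands for 0.20 × 4 × 26.13 = 20.9 points, about four times the target and about twice the 10 points of natural recovery that section 4.4 expects between visits.

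**4. Power at N = 52.** For 5.3 points, λ = N·D²/(8σ²(1 − ρ)) = 0.535 and power is 11.1%. A simulation of 40,000 trials also gave 11.1%. For 5 points, power is 10.4%.

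**5. Range over the unstated correlation (σ = 26.13).**

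| ρ | Power, 5.0 points | Power, 5.3 points | Total N for 80%, 5.3 points |
|---|---|---|---|
| 0 | 7.7% | 8.0% | 1,530 |
| 0.3 | 8.8% | 9.3% | 1,072 |
| 0.5 | 10.4% | 11.1% | 766 |
| 0.7 | 14.1% | 15.3% | 460 |
| 0.8 | 18.8% | 20.6% | 308 |
| 0.9 | 32.8% | 36.1% | 156 |

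For 5.3 points, 80% power with 52 patients would need ρ of about 0.967, or an SD of about 6.7 at ρ = 0.5.

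**6. A check that needs no correlation.** In a two-sample t-test at T2 with 26 per arm, the standard error is 26.13 × √(2/26) = 7.25. Power is 11.1% for 5.3 points and 10.4% for 5. The 95% confidence interval half-width is 2.009 × 7.25 = 14.6 points.

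**7. What 52 can detect with 80% power.** About 20.7 points at ρ = 0.5. Since this scales with √(2(1 − ρ)), it is 24.5 points at ρ = 0.3 and 9.3 at ρ = 0.9.

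**The case against.** Nothing in the protocol converts d to f or gives another basis for 52. The case on the other side concerns how firm the 11% is.

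- **The SD may be too large.** The pooling formula includes the squared difference between two means, so 26.13 can exceed the SD at a single visit. If it pooled two equal-sized time points 10 points apart, the within-visit SD would be √(26.13² − 5²) ≈ 25.6, which changes little. An assumed SD of 20 gives 10% to 55% for 5.3 points as ρ runs from 0 to 0.9. An assumed SD of 15 with ρ = 0.9 does reach about 80% for 5.3 points (75% for 5). But an SD of 15 would need pooled means about 43 points apart, and the protocol supports neither value.
- **The lead may already exist at T1.** Training ends at cast removal, the Summary calls the design post-test only, and section 10.4 expects benefit once the cast is off. The interaction is then smaller than 5 points and its power lower still. The T2 comparison gives 10–11%, and the group main effect 12–13% at ρ = 0.5.
- **Covariates and adjustment for T1.** Section 7.1.3 plans covariates. If they explained an assumed 20–50% of the variance, T2 power for 5.3 points would be about 13–17%. Adjusting for the T1 score gives 13% at ρ = 0.5 and 38% at ρ = 0.9.
- **A simpler conversion, f = d/2.** The unrounded 0.1014 gives 30% power and N = 194; the rounded 0.10 gives 29% and N = 200.
- **How a null result will be read.** The protocol does not say, so misreading is a risk and not a certainty.

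These points justify quoting a range and stating the assumptions. None restores 80% at the protocol's own inputs.

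**Conclusion.** The concern holds. The total of 52 comes from using a standardised mean difference as Cohen's f, and the reproduction is exact. At the protocol's SD of 26.13, power for its own target is 10.4% (5 points) to 11.1% (5.3 points), or about 1 chance in 9 for 5.3 points. For the interaction test these figures assume ρ = 0.5 and no group difference at T1. The comparison at T2 alone gives the same figures without either assumption. At 26.13, power stays at or below 36% for correlations up to 0.9. Because the confidence interval half-width at T2 is about 14.6 points, a null estimate could not exclude the 5-point target. The stated power for the primary outcome is wrong by a factor of about seven and must be corrected.

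**What to change.** In section 4.4, state that 0.20 is a standardised mean difference and that the matching f is 0.05. State that 52 patients give about 11% power for 5.3 points (10.4% for 5) at SD 26.13 and ρ = 0.5, and 80% power only for about 21 points. Give the assumed correlation and the assumption about T1.

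In section 9, add that the PRWHE result will be reported as a between-group difference with its 95% confidence interval, set against the 5-point target. Add that a non-significant result will not be read as showing no 1-week lead.

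The cost is protocol wording and a much less favourable power statement. The correction needs no added recruitment, which matters because section 7.2 reports 2.5 years of inclusion and a 35% response in the experimental group. It discloses the low power and does not raise it; whether to reconsider the sample size or the target is a separate decision for the sponsor.

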5. TREATMENT OF SUBJECTS

5.1 Investigational product/treatment

The treatment that the experimental group receives is motor imagery training, in addition to the regular treatment. The control group receives regular treatment only. Motor imagery is the mental state in which an individual performs an activity mentally and explicitly feels himself performing it, without actually performing the activity physically (47). This mentally rehearsing of a task can be done with two different strategies, by visual or kinetic motor imagery. When a person imagines the movement from a third person perspective, it is called visual motor imagery. When a person imagines the movement from a first person perspective, as if they are performing the movement themselves, it is called kinetic motor imagery (63). Research has shown that the neural structures activated during kinetic motor imagery are more similar to the neural structures activated during movement execution, than when visual motor imagery is performed (64,65). For that reason, the imagery training of DRF-patients in the present study will consist of kinetic imagery.

Potential participants are informed about this study by sending them an information letter, directly after their initial hospital visit. Patients who want to participate, return an informed consent by mail. When the patients who are willing to participate visit the hospital for a medical check one week after initial treatment, they are asked to fill in the VMIQ, because the VMIQ-score is an important inclusion criterion. When the patients reach the inclusion criteria, they are included in this study. After that, they receive information about the measurements and patients in the experimental group receive also instructions about the motor imagery training. The patients in the experimental group do the motor imagery training at home, unsupervised. The training starts with 1 minute of relaxation, where the patients are seated comfortably in a quiet environment, with their eyes closed. Such relaxation has proven to be promote the concentration, and as a consequence, the vividness of motor imagery (66). After that, the motor imagery training starts for about 6 minutes. This is well within the recommended maximal duration of 20 minutes, and long enough to be effective, as research has shown that the longer the imagery training session takes, the smaller the beneficial effect is (67). The patients imagine flexion, extension, abduction, adduction, pronation and supination of their injured wrist, following the procedure as explained during the instruction. Each set of movements (i.e. flexion-extension, adduction-abduction, pronation-supination) is executed in blocks of 10 repetitions.

The series of movements (10 times flexion-extension, 10 times adduction-abduction, 10 times pronation-supination) is repeated three times. The patients are asked to follow this procedure 4 times a day, which will take about 28 minutes a day.

5.2 Use of co-intervention

Patients in the experimental group will do the motor imagery training in addition to the usual medical treatment and a usual session of advice by a physiotherapist, which patients receive after cast removal. The patients in the control group will receive usual medical treatment and session of advice by a physiotherapist, but no motor imagery training. This single session of advice by a physiotherapist, is part of the standard treatment protocol for DRF's. The DRF-patients receive tips how to handle their casted hand. DRF-patients do not receive physiotherapy during the immobilization period. Thereby, only DRF-patients with complications or with severe affected hand function long term (> 2 weeks) after the immobilization period, will be advised to visit a physiotherapist. So, the patients who will be included in the current study, will not receive physiotherapy during the study.

After the last measurements, all patients will be asked whether they followed other interventions or received other treatments during the study period. If this is the case, the results of that patient will not be included in the statistical analysis, to control for confounding effects.

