7.2 Randomization, blinding and treatment allocation

Potential participants are randomly allocated to the experimental or control group before the start of the study, i.e. before inclusion. In this way, the potential participants allocated to the control group can receive other information about this study than potential participants allocated to the experimental group. This is done to prevent occurrence of the bias that might be present when the patients in the control group are aware of the working mechanism of motor imagery, and its potential benefits. When the patients in the control group know that they participate in a study that is conducted to determine whether motor imagery can promote the recovery after DRF, it is possible that they perform motor imagery during the immobilization, or pay more attention to their injured hand as normal. Such bias cannot be detected and may severely confound the results of this study. Therefore, we decided to keep the patients in the control group ignorant.

Because randomization is performed before inclusion, it is likely that some patients will decide not to participate, reducing the number of participants in that group. The experience of 2.5 years inclusion teaches us that the response rate to participate is different for each group (experimental group 35%, control group 62%). Therefore, the number of patients who will be asked to participate is controlled for this difference. This means that more patients are allocated to the experimental group, than to the control group. The random allocation is performed with remaining equal group sizes, and equal distribution of the different fracture types (intra-articular vs. extra-articular distal radius fractures).

The randomization process is done using PASW Statistics 18. Subject numbers are randomly allocated to the experimental or the control group. The order in which the patients receive their initial treatment determines their subject number. There is no blinding of the patients, nor the researcher is blinded.

Based on national statistics concerning the diseases and injuries diagnosed on a yearly basis, it is expected that 6-7 DRF-patients will be treated in the UMCG every week, and 2-3 of them will be women of 45-75 years of age (58).

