Three weeks later, which is 4 weeks after injury, the patients return to the hospital to remove the cast. At that moment, the first measurements will be performed. All tests will be performed by the study coordinator. Directly after cast removal, when they are still at the hospital, dexterity, the level of pain and pain relief, grip strength and range of motion will be determined. The PRWHE will be performed one day later by phone. Two weeks after cast removal, the second measurements will be conducted. Function, dexterity, the level of pain and pain relief, grip strength and range of motion will be measured.

The measurements will take place in the University Medical Center Groningen. The PRWHE and the VAS can be scored by the patients themselves, while the measurements with the SODA, goniometer and dynamometer will be conducted by the study coordinator. It is expected that the first measurements will take 30 minutes to complete, and the second measurements 35 minutes.

As explained in chapter 7.1, function is measured using the PRWHE. The PRWHE is a self-reporting instrument that determines the level of disability during specific and usual activities, and also contains some items to determine the level of pain and aesthetics (59). It takes on average 4 minutes to complete the questionnaire (61).

A digital goniometer is used to determine the active ROM. It is expected that the process of measuring ROM takes 6 minutes to complete.

Grip strength is measured using a hydraulic dynamometer (73). The strength of four different grips will be determined, according to the protocol as described by Mathiowetz et al. (1984). It is expected that the procedure to measure the grip strengths takes 4 minutes to measure both sides.

Dexterity is determined using the SODA. The SODA is a performance-based test, which measures the level of disability during activities of daily living (68). We expect that it takes 20 minutes to complete it. Instructions of the SODA will be given according to the protocol described by Van Lankveld et al. (1996).

The level of pain and the level of pain relief are determined using a VAS (75), a self-reporting scale. It is expected that it only will take a few seconds to complete it.

7.4 *Withdrawal of individual subjects*

The patients are free to withdraw from the study at any time, for any reason, and without consequences. Patients are withdrawn when the study coordinator thinks that participation by a

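### Section 5.2 drops patients who report another treatment from the analysis, while section 9.3 promises intention to treat; the exclusion follows allocation and can bias the comparison in either direction

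*Combined protocol and SAP*

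**What the plan says.** Section 5.2 (Use of co-intervention) sets a data-collection step: "After the last measurements, all patients will be asked whether they followed other interventions or received other treatments during the study period". It then gives the consequence: "If this is the case, the results of that patient will not be included in the statistical analysis, to control for confounding effects".

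Section 9.3 (Multivariate analysis) says: "The data of the patients in both groups will be analyzed using an intention to treat analysis". It makes no exception for co-intervention. Section 7.6 keeps patients who stop the training in follow-up, which fits section 9.3 rather than section 5.2.

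Three other statements bear on the point:

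- Allocation comes early (section 7.2): "Potential participants are randomly allocated to the experimental or control group before the start of the study, i.e. before inclusion".
- The trial is open (section 7.2): "There is no blinding of the patients, nor the researcher is blinded".
- On physiotherapy, section 5.2 says "only DRF-patients with complications or with severe affected hand function long term (> 2 weeks) after the immobilization period, will be advised" to see a physiotherapist, and concludes: "So, the patients who will be included in the current study, will not receive physiotherapy during the study". The second and last assessment (T2) is at two weeks (section 7.3): "Two weeks after cast removal, the second measurements will be conducted".

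**The concern.** The two rules cannot both govern the primary analysis. A patient who reports another treatment is in the set under section 9.3 and out of it under section 5.2. Nothing labels the exclusion as a per-protocol or sensitivity analysis, so either set could be defended after the data are seen.

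The reason given for the exclusion is control of confounding. Randomization protects the comparison of patients as allocated. Removing patients for something that happened afterwards can undo that protection if the event is related to recovery or differs by arm. Whether it is so related is an inference, since the documents do not say. Complications and care that patients seek themselves are possible reasons within the study window.

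Three features leave room for discretion: the question is asked after the outcomes are collected, the arm is known to everyone involved, and the treatments that trigger exclusion are not defined. What is at stake is the primary PRWHE comparison. The estimated benefit may be diluted, or a difference may appear where none exists.

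**Working it through.** **Inputs from the document (section 4.4).** SD 26.13 points; modelled one-week gain 5.3 points (rounded there to 5); effect size 0.20; two-sided alpha 5%; total 52 patients, about 26 per arm. A lower PRWHE is better.

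**The plan's own figure.** 5.3/26.13 = 0.203. For the within-between interaction with f = 0.20, two groups, two measurements, and assumed defaults of correlation 0.5 and epsilon 1, the noncentrality is λ = f²·N·m/(1−ρ) = 0.04 × 52 × 2/0.5 = 8.32 on (1, 50) degrees of freedom. Power is 80.7%, so 52 reproduces. (Whether 0.20 belongs in that formula is a separate question.) The calculation contains no allowance for excluded patients.

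**Assumptions for the bias calculation.** The documents give no exclusion rate, so the following are assumed: normal scores, the SD above in both arms, true difference 5.3, and exclusion linked to poor T2 function.

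*Case 1: every patient above a common cut is dropped.* Let p be the share of controls dropped. The cut is c = 26.13·z(1−p). In an arm with mean μ (0 for control, −5.3 for experimental), put a = (c−μ)/26.13. Exclusion lowers the arm mean by 26.13·φ(a)/Φ(a).

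Worked example, p = 0.10: c = 26.13 × 1.2816 = 33.49.
- Control: a = 1.2816, shift = 26.13 × 0.1755/0.90 = 5.10.
- Experimental: a = (33.49 + 5.3)/26.13 = 1.484, 6.9% dropped, shift = 3.72.
- Remaining T2 difference: 5.30 − 5.10 + 3.72 = 3.92.

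For the change from T1 to T2, each shift is multiplied by (1−ρ), where ρ is the T1–T2 correlation, assumed 0.5.

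| Controls dropped | Experimental dropped | T2 difference | Change difference (ρ = 0.5) |
|---|---|---|---|
| 2% | 1.2% | 4.84 | 5.07 |
| 5% | 3.2% | 4.42 | 4.86 |
| 10% | 6.9% | 3.92 | 4.61 |
| 15% | 10.8% | 3.55 | 4.43 |
| 20% | 14.8% | 3.25 | 4.27 |

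The loss against 5.3 is 9% to 39% at T2 and 4% to 19% on change. In the 20% row the change difference is 3.86 with ρ = 0.3 and 4.68 with ρ = 0.7. If only half of those above the 20% cut are dropped (10.0% of controls, 7.4% of experimental), the T2 difference is 4.50.

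*Case 2: no true effect.*
- The same 10% dropped in each arm: the shifts cancel and the bias is 0.
- Worst 10% of one arm and worst 5% of the other: 5.095 − 2.837 = 2.26 points at T2, and 1.13 on change with ρ = 0.5. If the control arm loses more, the bias is against motor imagery; if the experimental arm loses more, it favours motor imagery.
- Extreme bound, worst 10% of one arm only: 5.10 at T2, 2.55 on change.

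*Type I error.* A simulation with 26 per arm, 40,000 runs and nominal 5% gave, for T2 and change respectively: 5.1% and 5.1% (10% against 10%); 6.1% and 5.4% (10% against 5%); 10.4% and 6.6% (10% against none).

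*A second method.* Dropping a share q whose mean is D points worse than the arm mean shifts that arm by q·D/(1−q). With D = 26.13 and no true effect, 20% against 5% gives 26.13 × (0.25 − 0.0526) = 5.2 points; 15% against 5% gives 3.2. With D half as large, the results are 2.6 and 1.6. The sign again depends on the arm.

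**Secondary cost.** On the plan's own inputs, losing 10% (47 patients left) takes power from 80.7% to 76.5%; losing 20% (42 left) takes it to 71.6%.

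**The case against.** The strongest counter-argument is that few patients may be affected, and not for the reason modelled. Referral for severely affected function applies beyond two weeks after immobilization, so at or after T2, and section 5.2 expects no physiotherapy during the study. Section 4.3 excludes complications likely to worsen function. Section 7.2 keeps controls unaware of motor imagery, which weakens one motive for seeking extra care, and section 7.3 gives both arms weekly calls. At 26 per arm one patient is 3.8% of the arm, so the 10% to 20% rows may be too high. At 2% to 5% the loss on change is only 0.2 to 0.4 points. The 1.1-point bias on change is small beside a standard error of 26.13 × √(2/26) = 7.2 points, and the simulated type I error there is 5.4%. When both arms share a cut, the effect shrinks, which is conservative.

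Most of this stands as a limit on size. The extreme bound should carry no weight, and the documents offer no evidence that exclusion would differ by arm. It does not remove the contradiction. The protocol itself foresees other treatments, since it has a rule for them. Self-sought care is not restricted, and the two-week limit may not apply to complications.

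A further fair point is that, because allocation precedes consent (response 35% in the experimental group against 62% in control, section 7.2), an analysis of all included patients is still not an analysis of everyone allocated. That is a separate matter, which the fix below does not settle.

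**Conclusion.** The concern holds and must be fixed. What is certain is that sections 5.2 and 9.3 prescribe different analysis sets for the primary outcome, and that the section 5.2 rule removes patients on an event after allocation, ascertained after the outcomes in an open trial. That alone warrants the correction.

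The size of any bias is conditional. It rests on assumed exclusion rates, normality, a link between exclusion and poor T2 function, and, for change scores, an assumed correlation. It runs from zero, through a few tenths of a point at low rates, to about 2 points at T2 at the upper end of the common-cut range or with moderately unequal exclusion. Larger values need strongly unequal exclusion. The direction cannot be known from the documents.

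**What to change.** Replace the exclusion sentence in section 5.2 with wording such as:

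> Other treatments are recorded and reported by arm. All included patients stay in the primary analysis in their allocated arm. An analysis without patients who received other treatments is a sensitivity analysis.

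State before the analysis which other treatments count for that sensitivity analysis. Section 9.3 should carry the same definition of the primary set. Because allocation precedes consent, it should describe that set as all included patients rather than imply that it covers everyone allocated.

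The cost is a change of protocol wording and one extra sensitivity analysis. No additional patients, visits or measurements are needed, and patient care does not change.
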